3. PARTICIPANT SELECTION

3.1 Inclusion Criteria

- 3.1.1 Participants must have histologically or cytologically confirmed invasive breast cancer, with either locally advanced or metastatic disease. Patients without pathologic or cytologic confirmation of metastatic disease should have unequivocal evidence of metastasis from physical examination or radiologic evaluation.
- 3.1.2 Either the primary invasive tumor and/or the metastasis must be triple-negative, defined as:
 - hormone-receptor poor, ER- and PR-negative, or staining present in <1% by immunohistochemistry (IHC)
 - HER2-negative: 0 or 1+ by IHC, or FISH<2.0

- 3.1.3 Participants must have at least one lesion that is not within a previously radiated field that is measurable on computerized tomography (CT) or magnetic resonance imaging (MRI) scan per RECIST version 1.1. Bone lesions are not considered measurable by definition. See Section 11 for the evaluation of measurable disease.
- 3.1.4 Prior chemotherapy: Patients may have received 0-1 prior chemotherapeutic regimen for metastatic breast cancer and must have been off treatment with chemotherapy for at least 21 days before enrollment in the study. The number of patients with 0 prior chemotherapeutic regimen will be limited to a maximum of n = 20.
- 3.1.5 Prior biologic therapy: Patients must have discontinued all biologic therapy at least 21 days before participation.
- 3.1.6 Prior radiation therapy: Patients may have received prior radiation therapy in either the metastatic or early-stage setting. Radiation therapy must be completed at least 14 days prior to study participation and patients should have recovered from adverse effects of radiation to grade ≤1.
- 3.1.7 Age ≥ 18
- 3.1.8 ECOG performance status ≤1
- 3.1.9 Participants must have normal organ and marrow function as defined below:
 - Absolute neutrophil count ≥1500/mm³
 - Platelets $\geq 100.000/\text{mm}^3$
 - Hemoglobin ≥9 g/dL
 - Total Bilirubin ≤1.5 mg/dL
 - Serum creatinine ≤1.5 mg/dL OR measured creatinine clearance (CrCl) ≥45 mL/min as calculated by the Cockcroft-Gault method OR 24-hour measured urine CrCl ≥45mL/min
 - Alanine aminotransferase (ALT) and aspartate aminotransferase (AST) ≤2.5 times the upper limit of normal. For patients with documented liver metastases, AST/ALT ≤ 5.0 times the upper limit of normal.

- 3.1.10 Patients on bisphosphonates may continue receiving bisphosphonate therapy during study treatment.

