5.2 Pre-Treatment Criteria

5.2.1 Cycle 1, Day 1

- ANC must be $\geq 1500/\text{mm}^3$
- Hemoglobin must be $\geq 9 \text{mg/dl}$
- Platelets must be $\geq 100,000/\text{mm}^3$
- Serum creatinine < 1.5mg/dl OR measured creatinine clearance (CrCl) ≥45 mL/min as calculated by the Cockcroft-Gault method OR 24-hour measured urine CrCl ≥45mL/min
- SGOT/SGPT must be $\leq 2.5 \text{ X ULN}$ ($\leq 5 \text{ X ULN}$ if known liver metastases)
- Total Bilirubin ≤1.5 mg/dL

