5.2.2 Subsequent Cycles

- ANC must be $\geq 1000/\text{mm}^3$
- Hemoglobin must be ≥9mg/dl
- Platelets must be $\geq 75,000/\text{mm}^3$
- Serum creatinine ≤1.5 x ULN, or measured creatinine clearance (CrCl) ≥45 mL/min as calculated by the Cockcroft-Gault method or 24-hour measured urine CrCl ≥45mL/min
- Transaminitis must return to \leq grade 2
- Diarrhea must be resolved \leq grade 1.
- Nausea and Vomiting must return to ≤ grade 1
- Neurosensory must be \leq grade 2
- Other Treatment Related non-Hematologic Toxicity must return to ≤ grade 1

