• Diarrhea: Diarrhea should be treated promptly with appropriate supportive care, including administration of an anti-diarrheal agent according to standard practice guidelines. Anti-diarrheal agents should not be taken prophylactically. Patients should be instructed to begin taking anti-diarrheal medication at the first sign of: 1) poorly formed or loose stool, 2) occurrence of more bowel movements than usual in one day or 3) unusually high volume of stool. Anti-diarrheal agents should be deferred if blood or mucus is present in the stool or if diarrhea is accompanied by fever. In this setting, appropriate diagnostic microbiologic specimens should be obtained to exclude an infectious etiology. Patients should also be advised to drink liberal quantities of clear fluids to help prevent dehydration. Octreotide can also be considered to aid with management of diarrhea. If diarrhea is severe (ie. requiring IV hydration) and/or associated with fever or grade 3 or 4 neutropenia, broad spectrum

antibiotics should be considered. Additionally, hospitalization for IV hydration and eletrolyte correction should be considered.

Patients should be instructed to notify the Investigator or research staff for the occurrence of blood or black stools, symptoms of dehydration, fever, inability to take liquids by mouth, and inability to control diarrhea within 24 hours of using loperamide or other prescribed antidiarrheal medications.

- **Anemia**: Transfusions and/or erythropoietin may be utilized as clinically indicated for the treatment of anemia, but should be clearly noted as concurrent medications.
- **Neutropenia**: Colony-stimulating factors including G-CSF, pegylated G-CSF or GM-CSF according to Institutional Standards.
- **Febrile Neutropenia:** Patients experiencing febrile neutropenia with significant symptoms should be managed in a hospital setting according to standard procedures, with the urgent initiation of IV antibiotic therapy. Patients with febrile neutropenia without symptoms should be managed according to standard guidelines.
- Thrombocytopenia: Transfusion of platelets may be used if clinically indicated.
- Patients requiring radiation or surgery for palliation of a non-target lesion that have not measurably increased in size according to RECIST will be considered to have progressed.
- Participants may receive intravenous fluids on study.
- Bisphosphonates are allowed while on study.

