6.2 Dose Delays and Modifications for Cisplatin

Cisplatin will be initially administered at a dosage of 75mg/m² as an IV infusion given every 3 weeks. Patients who experience a Grade 3 or 4 toxicity attributable to cisplatin will have their cisplatin dose reduced to per Table 6-2. Toxicities resulting in myelosuppression, renal insufficiency, ototoxicity, and marked nausea and vomiting are most commonly seen with cisplatin monotherapy. Assessments should be made immediately prior to the scheduled administration of the chemotherapy. If patient needs to discontinue cisplatin therapy, patient can be treated on protocol with AZD1775 monotherapy.

Table 6-2 DOSE MODIFICATION OF CISPLATIN

Dose Level	Cisplatin Dose
0	75mg/m^2
-1	60mg/m^2
-2	50mg/m^2

Dose delays and modifications are summarized in the toxicity table in Table 6-6.

No dose re-escalations are allowed on study, except where noted below.

Expected toxicities for Cisplatin:

Nephrotoxicity

The major dose-limiting toxicity of cisplatin is cumulative nephrotoxicity. Tubular necrosis of both proximal and distal renal tubules has been noted in 28% to 36% of subjects treated with a single dose of 50mg/m^2 . It is first noted during the second week after a dose and is manifested by elevations in BUN and creatinine, serum uric acid and/or a decrease in creatinine clearance. Renal toxicity becomes more prolonged and severe with repeated courses of the drug. Renal function must return to normal before another dose of cisplatin can be given. Nephrotoxicity can be reduced by IV hydration and mannitol diuresis.

Nausea and Vomiting

Cisplatin causes moderate to severe nausea and vomiting in almost all subjects treated. Nausea and vomiting usually begin within 1 to 4 hours after treatment and last up to 24 hours. Various degrees of vomiting, nausea, and/or anorexia may persist for up to 1 week after the treatment. Delayed nausea and vomiting (beginning 24 hours or after chemotherapy) has occurred with complete emetic control on the day of cisplatin therapy. The use of prophylactic and continuing antiemetic medication reduces these adverse effects.

Hypomagnesemia

Hypomagnesemia has been reported in subjects treated with cisplatin and is probably related to renal tubular damage. It may become severe enough to cause tetany. Generally, serum electrolytes return to normal levels when cisplatin is discontinued and supplemental electrolytes are administered.

Ototoxicity

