Ototoxicity has been observed in up to 31% of subjects treated with a single dose of cisplatin (50mg/m²) and is manifested by tinnitus and/or hearing loss in the high frequency range (4000 to 8000 Hz). Decreased ability to hear normal conversational tones may occur occasionally. Ototoxicity can be more severe in children than in adults and more frequent and severe with repeated administration. Hearing loss can be unilateral or bilateral and is usually not reversible. During treatment with cisplatin, it is necessary to monitor hearing at each visit as part of a standard physical exam.

Myelosuppression

Myelosuppression occurs in 25 to 30% of subjects treated with cisplatin. The nadirs in circulating platelets and leukocytes occur between days 18 and 23, with most subjects recovering by day 39. Leukopenia and thrombocytopenia are more pronounced at higher doses (>50 mg/m²). Anemia (a decrease in hemoglobin of 2 gm/100ml) occurs at approximately the same frequency and with the same timing as leukopenia and thrombocytopenia.

Neurotoxicity

Cisplatin neurotoxicity is characterized by peripheral neuropathies, which are sensory in nature but can also include motor difficulties such as reduced deep-tendon reflexes and leg weakness. The symptoms usually occur after prolonged therapy (4 to 7 months). Cisplatin therapy should be discontinued when serious neuropathy develops. The neuropathy, however, may progress

further even after discontinuation of treatment.

Hematologic Toxicity

Dose adjustment at the start of a subsequent cycle of therapy will be based on the neutrophil and platelet counts on day 1 of the cycle. ANC must be $\geq 1.0 \times 10^9 / L$ and platelets $\geq 75 \times 10^9 / L$ before the start of each cycle. Treatment should be delayed to allow sufficient time for recovery. Upon recovery, if treatment is resumed, it should be accounting to the guidelines in Table 6-2 with respect to nadir platelet and ANC values for subsequent cycles, except as noted below. A delay in treatment due to hematologic toxicity if more than 3 weeks will result in withdrawal from the study.

The use of colony stimulating factors (filgrastim or pegfilgrastim) is permissible if recommended by the primary treating physician but should be clearly recorded in the medical record and case report form. Prophylactic use of GCSF is not recommended with the first cycle.

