Patients who develop treatment-related grade 3 non-hematological toxicity (except grade 3 transaminase elevations and nausea or vomiting) should have cisplatin therapy delayed until toxicity has resolved to less than or equal to grade 1 or baseline. Cisplatin will be continued at 60mg/m² for subsequent cycles. For grade 3 nausea, vomiting, or transaminase elevation, treatment will be delayed until toxicity resolves to grade 1 or less, and treatment may resume at 75 mg/m² dose. If any toxicity, including those described above, results in a three week treatment delay, patients will be taken off protocol. Patients with grade 4 non-hematological toxicity attributed to cisplatin will come off study unless exception is given by the Protocol Chair. Prior to retreatment, toxicity must resolve to less than or equal to grade 1 or baseline. For ≥ grade 2 Hgb toxicity, at the treating physician's discretion, dose may be reduced by one dose level in addition to transfusions and/or growth factor support as clinically indicated, with the option to re-escalate at physician's discretion. This should be documented in the medical record.

Table 6-6: Cisplatin Toxicity Management and Dose Modification Summary Table

Toxicity Event	Dose Modification	
Hematologic		
$ANC > 1000/mm^3$	None	
$ANC \geq 500/mm^3$	Delay until >1000/mm ³ and reduce to 60mg/m ²	
	(treat at 75mg/mm ² if initiating GCSF)	
$ANC < 500/mm^3$	Delay until >1000/mm ³ and reduce to 50mg/m ²	
	(treat at 60mg/mm ² if initiating GCSF)	
Grade 3 or 4 toxicity	Withdrawal from study or continue	
after 2 dose reduction		
Plt >100,000/mm ³	None	
Plt >50,000/mm ³	Delay until >75,000/mm ³ and reduce to 60mg/m ²	
$Plt < 50,000/mm^3$	Delay until >75,000/mm ³ and reduce to 50mg/m ²	
C 1 2 4	W'.1.11.C	
Grade 3 or 4 toxicity	Withdrawal from study	
after dose reduction		
Gastrointestinal		
Diarrhea		
Grade 3/4 or	Delay until resolution and reduce to 60mg/m ²	
requiring hospitalization		
Vomiting, Nausea		
Grade 3/4	Delay until ≤grade 1 or has returned to baseline and resume at	
	75mg/m ² or with one dose reduction (Per investigator discretion)	
Transaminases		
Grade 3/4	Delay until ≤grade 2 and with one dose reduction	
Neurological		
Neurosensory		
Grade 0-1	None	
Grade 2	Delay until resolves to ≤grade 1 and resume with one dose reduction	
Grade 3-4	Withdrawal from study	
Ototoxicity		
Tinnitus or	Reduce dose or withdraw from study at investigator discretion	
significant hearing loss		
Nephrotoxicity		
Cr <1.6 mg/dl or	None	

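### The hemoglobin minimum for starting a cycle is printed in mg/dl instead of g/dL in Sections 5.2.1 and 5.2.2, so as written it can never hold a dose

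*Combined protocol and SAP*

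**What the plan says.** Section 5.2 lists the conditions a patient has to meet before dosing: 5.2.1 for Cycle 1 Day 1 and 5.2.2 for all later cycles. The 5.2.2 list includes "Hemoglobin must be ≥9mg/dl". The 5.2.1 list carries the same number in the same unit.

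Two other places in the protocol state hemoglobin in grams. Eligibility criterion 3.1.9 requires "Hemoglobin ≥9 g/dL". The myelosuppression paragraph of Section 6.2 describes cisplatin anemia as "a decrease in hemoglobin of 2 gm/100ml"; 100 ml is one deciliter, so that is g/dL.

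The remaining hemoglobin and anemia text gives no level for redosing:

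- Under Hematologic Toxicity in Section 6.2, dose adjustment at the start of a later cycle "will be based on the neutrophil and platelet counts on day 1 of the cycle".
- The opening of Section 6.2 says "Patients who experience a Grade 3 or 4 toxicity attributable to cisplatin will have their cisplatin dose reduced".
- Under Other Toxicity in Section 6.2: "For ≥ grade 2 Hgb toxicity, at the treating physician's discretion, dose may be reduced by one dose level".
- Under supportive care in Section 5.4: "Transfusions and/or erythropoietin may be utilized as clinically indicated for the treatment of anemia".

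**The concern.** Section 5.2 is the list that site staff check before giving each dose, and its hemoglobin line is worded as a requirement. In the printed unit the requirement excludes nobody, so the one numeric hemoglobin rule for later cycles has no effect if followed literally.

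Anemia is an expected toxicity here. Section 6.2 reports myelosuppression in 25 to 30% of patients given cisplatin, and says anemia occurs at about the same frequency and timing as the falls in leukocytes and platelets, whose nadirs it places at days 18 to 23. With 21-day cycles, that window spans the next Day 1.

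The wording also matters for compliance. Treating a patient whose hemoglobin is under 9 g/dL is a deviation under the intended rule and is not one under the printed rule.

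**Working it through.** The check is a unit conversion followed by a search for any other rule that would supply the missing level. No sample-size, power or error-rate figure is involved.

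**Conversion.** Inputs: 9 mg/dl (Sections 5.2.1 and 5.2.2), 9 g/dL (Section 3.1.9), and 1 g = 1,000 mg.

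- Printed threshold: 9 / 1,000 = 0.009 g/dL.
- Ratio of the eligibility threshold to the printed one: 9 / 0.009 = 1,000.
- Illustration: a hemoglobin of 5 g/dL is 5 × 1,000 = 5,000 mg/dl, which passes a limit of 9 mg/dl easily.

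**Could the unit be a fault of text extraction?** Unlikely. The same unit appears in two separate lists that came through in different formats, while Section 3.1.9 shows g/dL intact.

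**Is there another numeric level for Cycle 2 onward?** Each candidate in turn:

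| Place | What it covers | Hemoglobin level for redosing? |
|---|---|---|
| 3.1.9 Eligibility | Entry to the study | 9 g/dL, but not re-applied at later cycles |
| 5.2.2, last item | Other treatment-related toxicity, non-hematologic only | None; anemia is outside it |
| 6.1 AZD1775 tables | Neutropenia and thrombocytopenia, plus non-hematologic toxicities | None; there is no anemia row |
| 6.2 opening | Cisplatin reduction for grade 3 or 4 toxicity | None; sets a dose, not a start level |
| 6.2 Hematologic Toxicity, Table 6-3 | ANC and platelets | None |
| 6.2 Other Toxicity | Hemoglobin toxicity of grade 2 or higher | None; by grade and discretionary |
| Table 6-6, hematologic rows | ANC and platelets | None |
| 5.4 Supportive care | Transfusion or erythropoietin | None; no numeric trigger |

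The only numeric hemoglobin rule for starting a later cycle is therefore the misprinted one. Section 5.2.2 is not specific to either drug and nothing in Section 6.2 waives it, so this is an error within a single rule, not a conflict between two rules.

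**Who could be affected?** A patient who enters at 9 to just under 11 g/dL and has the 2 g/dL fall described in Section 6.2 would be at 7 to just under 9 g/dL (9 − 2 = 7; 11 − 2 = 9). The intended rule would hold that patient's next cycle; the printed one would not. The documents do not say how many patients start in that range or how often hemoglobin falls below 9 g/dL, so no count can be given.

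**The case against.** The strongest reply is that this is a slip of the pen that nobody would act on. A limit no patient can fail is self-evidently a misprint. The correct unit stands in Section 3.1.9 beside the same number. The 5.2.1 list properly uses mg/dl for creatinine and bilirubin, so carry-over from neighbouring lines is a plausible cause. Table 6-6 has a similar slip in a cisplatin dose unit. All of this stands: it is a typographical error, not a chosen design feature, and the practical risk is low.

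The reply also holds largely for Cycle 1. Eligibility already requires 9 g/dL, and the Study Calendar puts baseline evaluations within one week of starting therapy. Only a fall between screening and Day 1 escapes, so the weight of the point rests on 5.2.2.

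It can further be said that anemia is managed in other ways: CTCAE grading, dose reduction for grade 3 or 4 toxicity attributed to cisplatin, discretionary reduction and transfusion, and a blood count on Day 1 of each cycle. One sentence under Other Toxicity in Section 6.2 requires recovery to grade 1 or baseline before retreatment. It directly follows the rule for grade 4 non-hematologic toxicity and most naturally belongs to it, although a wider reading is possible. These provisions narrow the consequence. None of them supplies a hemoglobin level at which a cycle must wait, so none repairs the printed rule.

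**Conclusion.** The point holds, as a minor one. Both start-of-cycle lists state the hemoglobin minimum at one thousandth of the evident intent, and for Cycle 2 onward no correct numeric value appears elsewhere. Read literally, the criterion cannot delay any cycle.

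This conclusion assumes that the intended limit is 9 g/dL, as the eligibility criterion indicates, and that the printed unit is the protocol's own. The number of patients whose dosing could have been affected cannot be estimated from the documents. The Simon two-stage design, its power and type I error, and the analysis of objective response rate are not affected.

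**What to change.** Replace mg/dl with g/dL in the hemoglobin lines of Sections 5.2.1 and 5.2.2. Nothing more is strictly needed.

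As an option, add one sentence to Section 6.2 stating that the 5.2.2 hemoglobin criterion has to be met before each cycle. The clinical team could use it to confirm that the criterion applies to both drugs and may be met by transfusion; Sections 5.4 and 6.2 already allow transfusion for anemia but do not link it to the start criterion.

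The cost is a unit correction in two places and, at most, one added sentence. No new assessment is required, because the Study Calendar already has a complete blood count on Day 1 of every cycle. If dosing has finished, the correction still belongs in a clarification note and in any later protocol that reuses this text.

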6. DOSING DELAYS/DOSE MODIFICATIONS

Dose delays and modifications will be made as indicated in the following table(s). The descriptions and grading scales found in the revised NCI Common Terminology Criteria for Adverse Events (CTCAE) version 4.0 will be utilized for dose delays and dose modifications. A copy of the CTCAE version 4.0 can be downloaded from the CTEP website http://ctep.cancer.gov/protocolDevelopment/electronic applications/ctc.htm.

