If GCSF is initiated, then the required dose modification will be adjusted according to the guidelines in footnote of Table 6-3.

Table 6-3
Dose Adjustments for Cisplatin Based on Hematologic Values for Preceding Cycle

Platelets (×1	0 ⁹ /L)	ANC (×10 ⁹ /L)	Dose of Cisplatin
≥75	and	≥1.0	75mg/m ^{2*}
≥50	or	≥ 0.5	60mg/m ^{2*} ,#
< 50	or	<0.5	50mg/m^{2*} ,@
Recurrence of	grade 3 or 4 th	rombocytopenia after 2 dose reductions	Withdraw subject from study
or			continue on ADZ1775
alone			
Recurrence of	grade 3 or 4 ne	utropenia after 2 dose reductions	Withdraw subject from study
or			
			continue on ADZ1775
alone			

^{*} Treatment should be delayed until recovery of platelets to $\geq 100 \times 10^9 / L$ and ANC to $\geq 1.0 \times 10^9 / L$.

Non-Hematologic Toxicity

For other grade 3 or higher non-hematologic effects (with the exception of grade 3 transaminase elevations and nausea or vomiting), treatment should be delayed until resolution (less than or equal to baseline). Treatment can be resumed at 60mg/m², if deemed appropriate by the treating physician, for all subsequent cycles.

Neurosensory Toxicity

[#] For ANC ≥0.5 treat at 75mg/m² dose if initiating GCSF

[@] For ANC<0.5 treat at 60mg/m² dose if initiating GCSF

Adjustments of the cisplatin dose in subjects with neurosensory toxicity are shown in Table 6-4. Cisplatin therapy should be held for grade 2 or higher neurosensory toxicity and should resume with a dose reduction once it has resolved to grade 1.

Table 6-4
Dose Adjustments for Cisplatin Based on Neurosensory Toxicity

CTCAE Grade	Dose of Cisplatin
0-1	100% of previous dose
2	60mg/m^2
3-4	Withdraw participant from study or continue on AZD1775
alone	

Tinnitus or Significant Hearing Loss

In cases of tinnitus or significant hearing loss, cisplatin therapy should be reduced or stopped, at the discretion of the investigator.

Nephrotoxicity

Cisplatin dose adjustments in subjects with renal toxicity are shown in Table 6-5. Either serum creatinine or estimated creatinine clearance may be used. If a dose delay or dose reduction occurs due to nephrotoxicity, subsequent doses of cisplatin may be escalated based on the renal function on the day of treatment (+/- 3 days) and should be determined based on Table 6-5.

Table 6-5
Cisplatin Dose Adjustments for Renal Toxicity

Creatinine(mg/dl)	OR Creatine Clearance(cc/min)	Dose of Cisplatin
<1.6	>50	75mg/m^2
1.6-2	10-50	60mg/m^2
>2	<10	Delay one week

Other Toxicity

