CrCl >50 cc/min		
Cr 1.6-2 mg/dl or	50mg/m ²	
CrCl 10-50 cc/min		
Cr>2 mg/dl or	Delay one week	
CrCl <10-cc/min		
Other Toxicity		
Grade 3	Delay until ≤ grade 1 or has returned to baseline and resume at	
	60mg/m^2	
·		

Grade 4	Withdraw from study, unless exception granted by the Principal
	Investigator

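### Tables 6-5 and 6-6 order different cisplatin doses (60 and 50 mg/m2) for the same renal impairment, and no text ranks either table against the Section 5.2.2 treatment criterion

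*Combined protocol and SAP*

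**What the plan says.** Section 5.2 lists pre-treatment criteria. From cycle 2 the renal criterion in Section 5.2.2 is "Serum creatinine ≤1.5 x ULN, or measured creatinine clearance (CrCl) ≥45 mL/min as calculated by the Cockcroft-Gault method", with a 24-hour urine CrCl of at least 45 mL/min as a further alternative. The limbs are joined by 'or', so treatment is withheld only when all of them fail.

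Section 6 opens by saying that delays as well as dose changes follow its tables. Section 6.2 adds: "Dose delays and modifications are summarized in the toxicity table in Table 6-6". It also fixes the timing: "Assessments should be made immediately prior to the scheduled administration of the chemotherapy".

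Two tables in Section 6.2 carry renal rows. Table 6-5, "Cisplatin Dose Adjustments for Renal Toxicity", gives 60 mg/m2 at creatinine 1.6-2 mg/dl or CrCl 10-50. Table 6-6 has the same row ("Cr 1.6-2 mg/dl or" / "CrCl 10-50 cc/min") but gives 50 mg/m2. In both tables the only renal delay ("Delay one week") comes at creatinine above 2 mg/dl or CrCl below 10.

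Three other statements bear on the point. The nephrotoxicity text with Table 6-5 lets either renal measure be used and bases later doses, after a renal delay or reduction, on Table 6-5. The list of expected toxicities in Section 6.2 says that renal function has to be back to normal before the next cisplatin dose. Section 5.1 refers to Section 6 for dose modifications without ranking the two.

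**The concern.** The two tables cannot both be followed. A site that opens the detailed table reduces by one dose level; a site that opens the summary reduces by two, for the same patient on the same day.

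The second issue is whether that patient should be treated at all. Section 5.2.2 and the tables are applied at the same moment, just before a cycle, and use different renal limits. Neither refers to the other. Where both serum creatinine and CrCl are impaired, 5.2.2 can withhold the cycle while the tables show a reduced dose and no delay.

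The protocol names cumulative nephrotoxicity as cisplatin's major dose-limiting toxicity and says it worsens with repeated courses. Cisplatin is given every cycle, so the stake is patient safety and uniform dosing between sites.

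**Working it through.** **1. The two tables side by side (no assumption needed)**

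| Renal values | Table 6-5 | Table 6-6 |
|---|---|---|
| creatinine <1.6 mg/dl or CrCl >50 | 75 mg/m2 | no change |
| creatinine 1.6-2 or CrCl 10-50 | 60 mg/m2 | 50 mg/m2 |
| creatinine >2 or CrCl <10 | delay one week | delay one week |

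In Table 6-2, 60 mg/m2 is level -1 and 50 mg/m2 is level -2. Relative to full dose, 60/75 = 80% and 50/75 = 67%. The gap is (60 - 50)/60 = 17%. At an assumed body surface area of 1.6-1.9 m2, 60 mg/m2 is 96-114 mg and 50 mg/m2 is 80-95 mg, a difference of 16-19 mg per dose.

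**2. Where Section 5.2.2 and the tables part**

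- 5.2.2 withholds if creatinine > 1.5 x ULN and CrCl < 45.
- Both limbs of the tables' middle row give a reduced dose if creatinine is 1.6-2 and CrCl is 10-50.
- Overlap: creatinine 1.6-2 and above 1.5 x ULN, with CrCl 10 to <45.

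The overlap is empty once 1.5 x ULN reaches 2.0, that is at ULN = 2.0/1.5 = 1.33 mg/dl. The documents give no ULN, so I assume a range of 0.9-1.4 and count the one-decimal creatinine values 1.6, 1.7, 1.8, 1.9 and 2.0:

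| Assumed ULN (mg/dl) | 1.5 x ULN | Creatinine values in the overlap (of 5) |
|---|---|---|
| 0.9 | 1.35 | 5 |
| 1.0 | 1.50 | 5 |
| 1.1 | 1.65 | 4 |
| 1.2 | 1.80 | 2 |
| 1.3 | 1.95 | 1 |
| 1.4 | 2.10 | 0 |

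This counts only patients whom both limbs of the tables would dose. A site using the CrCl column alone, as the text with Table 6-5 allows, would find a reduced dose at CrCl 10 to <45 whatever the ULN.

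**3. Can such patients occur?**

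Cockcroft-Gault for women is (140 - age) x weight x 0.85 / (72 x creatinine). For an assumed woman aged 60, 70 kg, creatinine 2.0: 80 x 70 x 0.85 / 144 = 33 mL/min. At ULN 0.9-1.3, 5.2.2 withholds, Table 6-5 gives 60 mg/m2 and Table 6-6 gives 50 mg/m2.

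For 16 assumed female profiles (age 40, 50, 60, 70 by weight 55, 65, 75, 85 kg), CrCl is 10 to <45 in 10, 10, 13, 13 and 14 profiles at creatinine 1.6, 1.7, 1.8, 1.9 and 2.0. That is 60 of 80 profile-creatinine pairs. Adding the ULN condition leaves 60, 60, 50, 27, 14 and 0 pairs for ULN 0.9, 1.0, 1.1, 1.2, 1.3 and 1.4. These counts show that the overlap is reachable; they are not patient frequencies.

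**4. How the blood-count rules are written**

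For neutrophils and platelets, Section 6.2 restates the 5.2.2 limits (1.0 and 75 x 10^9/L) as conditions for each cycle, and the reduced-dose rows of Table 6-6 tell the site to delay until recovery and then reduce. The reduced-dose renal row states a dose and nothing else.

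**The case against.** The strongest reply is that 5.2.2 and the tables work in sequence. One section is headed as pre-treatment criteria and the other table as dose adjustments: the first decides whether to treat, the second how much. The reduced-dose row still has work to do under that reading, for patients who pass 5.2.2 on one limb while the other measure is impaired. The sentence requiring renal function to return to normal also favours withholding. Much of this stands. A reader might infer that the protocol directs sites to dose patients whom 5.2.2 excludes, or that the tables override it. The documents do not support that: no table row says to treat a patient who fails 5.2.2, and no sentence gives the tables precedence.

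What remains is that the natural reading is not written down and some text pulls the other way: Section 6 assigns delays to its tables, their renal delay row is laxer than 5.2.2, and the reduced-dose renal row lacks the delay wording of the blood-count rows. The return-to-normal sentence does not settle it, because taken literally it contradicts the tables' reduced-dose row as well.

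Two further replies limit the size. The overlap depends on a ULN that the documents do not give. And because 5.2.2 uses 'or', it already admits some patients with low CrCl. With an assumed ULN of 1.1, a woman aged 70, 55 kg, creatinine 1.6 (limit 1.65) has CrCl 70 x 55 x 0.85 / (72 x 1.6) = 28 mL/min; she passes 5.2.2 and is dosed. Ranking the rules does not change that.

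None of this touches the 60 against 50 mg/m2 mismatch. The direction to use Table 6-5 for later doses narrows the doubt for those cycles and suggests which figure was meant, but the summary table still prints the other.

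**Conclusion.** The dose mismatch is certain: for identical renal values the two tables differ by one dose level, 17% of the higher dose. It rests on no assumption and should be corrected.

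The conflict with Section 5.2.2 is real but conditional. It requires a local ULN below about 1.33 mg/dl, creatinine 1.6-2 mg/dl and above 1.5 x ULN, and CrCl 10 to <45. Within those limits it is a missing statement of precedence, with a safe natural reading that sites are not told to adopt. How many patients it would affect cannot be derived from the documents.

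A reader might also infer that the trial's efficacy results are compromised. Nothing in the documents shows an effect on ORR or PFS, and none is claimed. This is a matter of patient safety and consistent dosing.

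**What to change.** 1. Use one reduced renal dose in Tables 6-5 and 6-6. The default is 60 mg/m2, because Section 6.2 bases later doses on Table 6-5, unless the sponsor confirms that 50 mg/m2 was intended.
2. Above both tables add: 'The Section 5.2.2 renal criterion must be met before a cycle starts; these tables set the cisplatin dose only once it is met.' Add 'Section 5.2.2 renal criterion not met' to the delay row of both tables, and apply that row first. The wording refers to the cycle, not only to cisplatin, because 5.2.2 governs the cycle.
3. Keep the reduced-dose row for all other patients with creatinine 1.6-2 or CrCl 10-50. Raising its lower edge to 45 would leave patients who pass 5.2.2 on creatinine with CrCl 10-44 without a dose. Word the top row as 'no renal dose reduction', not as 75 mg/m2, so that reductions made for other toxicities stand; Section 6.2 generally bars re-escalation.
4. Leave to the sponsor how the return-to-normal sentence is reconciled with these rules. Relaxing it is a clinical decision.

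The cost is a wording amendment. Weight and serum creatinine are already collected on Day 1 of each cycle (Section 10), so Cockcroft-Gault CrCl needs no new test. The downside is an occasional treatment delay, which counts toward the limit in Section 5.5: a toxicity delay of more than 21 days ends protocol therapy.
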